# 9.2.3 Registry Study Population

Paediatric and adult participants with FOP who are enrolled in the FOPal registry and have received at least one dose of palovarotene, prescribed, as per local label, by their treating physician will be included in the palovarotene-exposed cohort. Participants never treated with palovarotene will be included in the palovarotene-unexposed cohort.

To be enrolled, participants must comply with all the inclusion criteria (Section 9.2.1.1 and Section 9.2.2.1 for the palovarotene-exposed and unexposed cohorts, respectively) and exclusion criteria (Section 9.2.1.2 and Section 9.2.2.2 for the palovarotene-exposed and unexposed cohorts, respectively).

PAGE 38 OF 287

The FOPal registry study aims to enrol a minimum of 67 participants with FOP treated with palovarotene (exposed) and 33 participants with FOP not treated with palovarotene (unexposed) from countries/sites willing to participate. Approximately half of the participants in each cohort (exposed and unexposed) will be paediatric (8 years to less than 18 years of age for girls and 10 years to less than 18 years of age for boys).

# 9.2.4 Registry Study Duration

The duration of the FOPal registry study is up to 11 years, with an enrolment period of maximum 10 years from first participant, first visit, and a minimum of 1 year of data collected for participants who are enrolled within that period.

Participant enrolment will start on the date that palovarotene is commercially available in any given country for exposed participants, and once the investigational site has been activated for all participants.

The investigator must ensure that the participant receives appropriate medical follow-up and this should be properly documented in the participant's medical records and eCRFs regarding:

- AEs or their sequelae (any AE, based on the investigator's opinion, not only those assessed as related) that persist after the date of palovarotene discontinuation for exposed participants.
- Medical events of special interest (growth outcomes, including PPC, and fractures) for unexposed participants for the entire study duration.

## 9.2.5 Registry Study Location

Exposed participants will be recruited in countries/sites willing to participate and where palovarotene is registered/marketed. Unexposed participants to palovarotene will be recruited in the same participating sites.

# 9.2.6 Registry Study Schedule

The schedule of assessments that will be collected during the FOPal registry study for exposed naïve, exposed non-naïve, and unexposed participants is summarised in Table 2, Table 3 and Table 4 respectively. As this is a non-interventional, observational, prospective and retrospective registry study designed to collect and assess real-world data, these assessments are not mandated by this protocol. If some assessments are not routinely performed by the investigator, the data will not be captured in the eCRF.

**PAGE 39 OF 287** 

 Table 2
 Schedule of Assessments: Exposed Naïve Participants

Assessment/Procedure	Baseline Visit	Follow-Up Visits (as per routine clinical practice[a])/ End of Study Visit
Clinic visit or telephone/video contact visit	X	X
Informed consent [b]	X	
Inclusion/exclusion criteria	X	
Baseline demographics	X	
Physical examination [c,d]	X	X
Medical or surgical history	X	
FOP history	X	
Growth status assessment (bone age, knee height and epiphyseal status) [d,e]	X	X
Tanner staging [d,e]	X	X
Linear height [f] and weight [d]	X	X
Vital signs [d,g]	X	X
Pregnancy testing [h]	X	X
Prior /concomitant medications [i]	X	X
Concomitant surgery and non-drug therapies	X	X
Prior use of palovarotene (investigational product)	X	
Palovarotene dose for chronic and flare-up treatment [j]	X	X
Spirometry and DLCO test [d,k]	X	X
CAJIS [d]	X	X
Movement mobility history (including flare-ups [1])	X	
Movement mobility changes (including flare-ups)	X	X
Spinal health assessment [m]	X	X
AEs, SAEs, Special Situations, and AESIs [n]	X	X
Participant Questionnaires:		
FOP-PFQ assessment [o]	X	X
PROMIS Global Health Scale [o]	X	X
FOP assistive devices assessment [o]	X	X

AE=Adverse Event; AESI=Adverse Event of Special Interest; CAJIS=Cumulative Analogue Joint Involvement Scale; CT= Computed Tomography; DLCO=Diffusion Capacity of the Lung for Carbon Monoxide; FEV1=Forced Expiratory Volume in one second; FOP=Fibrodysplasia Ossificans Progressiva; FOP-PFQ=FOP-Physical Function Questionnaire; FVC=Forced Vital Capacity; HEENT= head, eyes, ears, nose and throat; PI=Prescribing Information; PROMIS=Patient-Reported Outcomes Measurement Information System; SAE=Serious Adverse Event; SS=Special Situation.

**PAGE 40 OF 287** 

- a Follow-up Visits are recommended every 6 months, or as per local label.
- b If participant <18 years (or the legal age of consent in the jurisdiction in which the study is taking place), assent and parent or legally authorised representative consent will also be required.
- c This includes a general assessment, dermatologic, lymph nodes, HEENT, chest, cardiac, abdomen, limb/extremities, musculoskeletal, neurologic and other.
- d Not expected in the context of a telephone/video visit.
- e Collected for growing children. Assessment as per local label.
- f Linear height within 6 to 12 months prior to and at the Baseline Visit.
- g Vital signs to be collected are respiratory rate, blood pressure and heart rate.
- h Participants will be assessed for child-bearing status and pregnancy prevention measures. As per local label, pregnancy testing is carried out with a confirmation of absence of pregnancy monthly if the participant receives palovarotene and one month after stopping. These conditions also concern participants who are not currently sexually active unless the prescriber considers that there are compelling reasons to indicate that there is no risk of pregnancy.
- i This includes a period of two months prior to the signed informed consent date.
- i Not applicable for pregnant participants.
- k Spirometry obtains the lung function parameters of observed and % predicted FVC and FEV1 and the absolute and % predicted FEV1/FVC ratio. The DLCO test obtains observed and % predicted DLCO which provides information on the efficiency of gas transfer from alveolar air into the bloodstream.
- 1 This includes number of flare-ups over the past 12 months before the signed informed consent date.
- m Spinal health assessment to be performed using radiological imaging (e.g. CT, X-ray, scintigraphy, etc).
- n AE, SAE, Special Situation and AESI collection begins once the informed consent has been signed.
- o Paper-based patient-reported questionnaires.

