**PAGE 30 OF 287** 

#### 7.3.1 Safety Profile of Palovarotene

Safety data from the FOP clinical studies reflect exposure to palovarotene in a total of 164 participants, including 139 participants aged 8 years and above for females and 10 years and above for males ( $\geq 8/10$  years; the target population for the FOPal registry study) for a mean duration of 94.1 weeks, to a maximum of 3.8 years. Participants received either:

- Chronic/flare-up regimen 5 mg daily dose of palovarotene with a 20/10 mg dose for 12 weeks at the time of flare-up (4 weeks of 20 mg once daily followed by 10 mg once daily for 8 weeks);
- Flare-up regimen of either the 20/10 mg dose for 12 weeks, a 10/5 mg dose for 6 weeks (10 mg once daily for 2 weeks followed by 5 mg once daily for 4 weeks) or a 5/2.5 mg dose for 6 weeks (5 mg once daily for 2 weeks followed by 2.5 mg once daily for 4 weeks).

In palovarotene-exposed participants aged  $\geq 8/10$  years, the most commonly reported adverse reactions were in the *Skin and subcutaneous disorders* (97.8%), *Gastrointestinal disorders* (75.5%) and *Infections and infestations* (48.9%) System Organ Classes (SOC).

Participants <18 years with open epiphyses were assessed for growth during the clinical studies. PPC was identified in 27 of 102 participants (26%) <18 years of age and was more common in younger (<8/10 years: 14 of 25 participants, 56%) compared with older ( $\geq$ 8/10 to <14 years: 13 of 39 participants, 33%; and  $\geq$ 14 to <18 years: 0 of 38 participants, 0%) participants. In participants who received only chronic dosing, PPC, when observed, typically occurred between 12 and 18 months. The higher proportion of younger participants with PPC is not unexpected given that pre-adolescent individuals are not expected to have physiological growth plate closure. Thus, any narrowing, partial closure, or closure are likely to be assessed as premature by the clinician. However, the possibility that younger participants are predisposed to developing PPC or are more sensitive to the effects of palovarotene cannot be excluded.

Palovarotene treatment is currently indicated for children aged 8 years and above for females and 10 years and above for males (or as per the approved indication in locally approved label). However, children between the ages of 4 years and 8/10 years were included in the clinical studies and exposed to palovarotene. The safety profile for palovarotene in participants with

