**PAGE 44 OF 287** 

- \* Retrospective period starts 12 months preceding the signed informed consent but only from the time the child has reached the age of 8 years for girls and 10 years for boys.
- a Follow-up Visits are recommended every 6 months.
- b If participant <18 years (or the legal age of consent in the jurisdiction in which the study is taking place), assent and parent or legally authorised representative consent will also be required.
- c This includes a general assessment, dermatologic, lymph nodes, HEENT, chest, cardiac, abdomen, limb/extremities, musculoskeletal, neurologic and other.
- d Not expected in the context of a telephone/video visit.
- e Collected for growing children.
- f Vital signs to be collected are respiratory rate, blood pressure and heart rate.
- g Spirometry obtains the lung function parameters of observed and % predicted FVC and FEV1 and the absolute and % predicted FEV1/FVC ratio. The DLCO test obtains observed and % predicted DLCO which provides information on the efficiency of gas transfer from alveolar air into the bloodstream.
- h Paper-based patient-reported questionnaires.
- i Closest available value to 12 months preceding signed informed consent.
- j Previously unexposed participants starting palovarotene and remaining in FOPal should follow the exposed naïve participants schedule from the first marketed palovarotene intake (See Table 2 and Section 9.2.8).

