**PAGE 49 OF 287** 

#### 9.2.7.4 Follow-up Visits/End of Study Visit for Unexposed Participants

The participants will attend a clinic or telephone/video visit and assessments will be performed according to routine clinical care. For the FOPal registry study, the following variables will be captured from medical records as available:

- Physical examination;
- Growth status assessment for growing children (bone age, knee height and epiphyseal status, assessment as per local label);
- Tanner staging for growing children;
- Linear height and weight;
- Vital signs (respiratory rate, blood pressure and heart rate);
- Concomitant medications;
- Concomitant surgery and non-drug therapies;
- Spirometry and DLCO test;
- CAJIS for FOP;
- Number of flare-ups since Last Visit;
- Movement mobility changes;
- Medical events of special interest;
- FOP-PFQ;
- PROMIS Global Health Scale;
- FOP assistive devices assessment.

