- Birth and developmental outcomes through the infant(s)' first year of life.

For growing children with FOP exposed and unexposed to palovarotene:

- Raw values and change from Baseline in linear height and knee height velocity at each Follow-up Visit until skeletal maturity or final adult height is reached;
- Baseline linear height z-scores and change from Baseline at each Follow-up Visit until skeletal maturity or final adult height is reached;
- Mean difference between chronological age and bone age at each Follow-up Visit;
- Frequency, severity and descriptive details of PPC overall and at each Follow-up Visit.

For participants with FOP exposed to palovarotene:

- Mean dose/year for chronic treatment;
- Mean dose/cycle for flare-up treatment.

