## 9.3.2.6 *Medical Events of Special Interest for Unexposed Participants*

The FOPal registry will collect medical events within 12 months preceding the signed informed consent, at Baseline Visit and at the Follow-up/End of Study Visits if available.

Medical events of special interest include, but are not limited to:

- Growth outcomes, including PPC;
- Fractures.

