#### **Growth Status**

The FOPal registry study will collect bone age, knee height and epiphyseal status ("open/partially closed/closed/not assessable") for growing children at the Baseline Visit, at the first marketed palovarotene intake (for exposed non-naïve participants) and at the Follow-up/End of Study Visits if available.

Growing children are those in whom the growth plates have not fused. Whether the participant is a growing child is based on the investigator's assessment.

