**PAGE 76 OF 287** 

Any radiological or clinical fracture, or PPC, must be reported as serious (seriousness criteria should be "important medical event" if no other seriousness criteria are present (e.g. hospitalisation)).

Is a suspected transmission of any infectious agent via an authorised medicinal product

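### Premature physeal closure reaches the record by different routes in exposed and unexposed children, so reading the two frequencies side by side is open to differential ascertainment of unknown direction and size

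*Protocol*

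**What the plan says.** Section 9.3.1.2 lists, for growing children exposed and unexposed, "Frequency, severity and descriptive details of PPC overall and at each Follow-up Visit". Section 9.7.3.4 places its presentation under key safety outcomes.

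**Exposed children.** Note e to Tables 2 and 3 attaches to bone age, knee height and epiphyseal status: "Collected for growing children. Assessment as per local label". Note a lets visits follow the label instead of the recommended 6 months. Section 11, which by its title covers exposed participants, makes PPC an adverse event of special interest (11.1.4), requires reporting within 24 hours (11.2.2) and adds in 11.1.2: "Any radiological or clinical fracture, or PPC, must be reported as serious". Collection runs to last intake + 30 days (11.2.1).

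**Unexposed children.** Table 4's note is only "e Collected for growing children", and its note a gives 6-monthly visits without the label. Section 9.2.7.4, for follow-up visits of the same cohort, has "Growth status assessment for growing children (bone age, knee height and epiphyseal status, assessment as per local label". PPC is a medical event of special interest, collected "at Baseline Visit and at the Follow-up/End of Study Visits if available" (9.3.2.6). Section 9.2.4 nevertheless requires the investigator to document it for the entire study.

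**Both cohorts.** Section 9.2.6 says that the protocol mandates none of the scheduled assessments. Section 9.3.2.7 collects growth status at baseline, at first marketed intake ("for exposed non-naïve participants) and at the Follow-up/End of Study Visits if available"), with no restriction by cohort.

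**The concern.** PPC was seen in 26% of participants under 18 in the earlier studies, and section 7.3.1 names premature epiphyseal fusion as the one exception to a consistent safety profile across age groups. Readers of the final report will set the exposed and unexposed frequencies next to each other whether or not a formal contrast is printed.

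A closure that is not imaged, or is imaged but not called premature, does not enter a count of reported events. If the chance of being imaged, called and recorded depends on cohort, the two frequencies reflect surveillance as well as any drug effect. The call is also a judgement: the protocol provides for no central or exposure-blind reading, and section 9.3.2.7 leaves to the investigator whether a child is still growing. Section 7.3.1 acknowledges that in pre-adolescents "any narrowing, partial closure, or closure are likely to be assessed as premature by the clinician".

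Section 9.9 warns that data may be missing and that practice varies between sites. It does not say that ascertainment may vary with exposure.

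**Working it through.** **1. The plan's own figures (section 7.3.1).** 14/25 = 56.0%, 13/39 = 33.3%, 0/38 = 0%. The parts add up: 14 + 13 + 0 = 27 and 25 + 39 + 38 = 102, and 27/102 = 26.5%, printed as 26%. For the ages that can enrol here (from 8/10 to under 18 years) the figure is 13/(39 + 38) = 13/77 = 16.9%. These are treated children; the protocol gives no PPC frequency in untreated children.

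**2. The two routes side by side.**

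| Step | Exposed | Unexposed | Could raise the recorded frequency in |
|---|---|---|---|
| Stated driver of growth assessment | Local label (Tables 2 and 3, note e) | None in Table 4; local label in 9.2.7.4 | Exposed, if the label asks for more than routine care |
| Visit timing | 6 months or label | 6 months | Exposed, on the same condition |
| Assessment mandated by protocol | No | No | Neither |
| Growth data if available | Yes | Yes | Neither |
| Reporting of a PPC once found | Special interest, serious, 24 hours | Medical event of special interest, if available | Exposed |
| Collection period | To last intake + 30 days | Entire study | Unexposed |
| Who makes the call | Investigator, no blind reading stated | Same | Unknown |

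The rows do not all point the same way. The label's imaging schedule and the imaging rate in routine care are both absent from the protocol, so the net direction cannot be worked out from it.

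**3. How much it could matter (assumed values).** Let p be the same true risk in both cohorts, and let sE and sU be the probabilities that a closure ends as a PPC record in exposed and unexposed children. Then

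- apparent ratio = sE / sU
- apparent difference = p × (sE − sU)

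With sE = 1:

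| sU | Ratio | Difference at p = 5% (assumed) | at p = 16.9% (13/77) | at p = 33.3% (13/39) |
|---|---|---|---|---|
| 0.75 | 1.33 | 1.25 points | 4.2 points | 8.3 points |
| 0.50 | 2.0 | 2.5 points | 8.4 points | 16.7 points |
| 0.25 | 4.0 | 3.75 points | 12.7 points | 25.0 points |

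If the shorter exposed collection period dominates, the roles swap. With sU = 1 and sE = 0.75 or 0.50 the ratio is 0.75 or 0.50, and the differences have the same size with the opposite sign. No value of sE or sU is given in the protocol.

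**4. Precision.** Half of the planned minimum cohorts (9.7.2) is 67/2 = 33.5 exposed and 33/2 = 16.5 unexposed children. One missed or differently labelled closure moves the unexposed frequency by 1/17 = 5.9 points or 1/16 = 6.25 points. With no PPC recorded, the exact 95% upper limit is 1 − 0.025^(1/n): 19.5% for n = 17 and 20.6% for n = 16.

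**The case against.** The strongest answer is that the cohorts differ less than the notes to the tables suggest. Growth data are collected only if available, and nothing is mandated, in either cohort. The rule that PPC is serious governs what happens after a closure is found; it sends nobody to look for one. The investigator must document PPC in unexposed children for the whole study, whereas exposed collection stops 30 days after last intake, and a participant who stops treatment is withdrawn unless the reason is a safety concern or pregnancy (9.2.8). All of this stands. A reader might infer that the exposed frequency will be inflated, or that the two frequencies cannot be compared at all. The documents support neither reading.

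It can also be said that no PPC comparison is planned. This is right as far as it goes: the weighted comparison in 9.7.3.4 covers flare-ups, height velocity and z-scores, and bone fractures, with no hypothesis testing. PPC remains a two-cohort endpoint, so the point bears on how a descriptive table is read.

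The remark in 7.3.1 about calling closure premature explains an age pattern in treated trial participants, mainly below the ages that can enrol here. It shows that the call depends on what the clinician expects. It is not evidence that judgement differs by exposure.

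Finally, 9.7.3.4 already says that epiphyseal status and bone age will be analysed, and table details belong to the SAP. The data are therefore not ignored. What the protocol itself should settle is the conflict between 9.2.7.4 and Table 4, and the silence of 9.9.

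**Conclusion.** The concern holds in a limited form. The stated driver of growth assessment, the status of a PPC report and the length of collection all differ by cohort, and the call is made without a stated blind reading. Side-by-side PPC frequencies are therefore open to differential ascertainment. Its direction is uncertain because the differences pull both ways, and its size cannot be estimated from the protocol. The ratios of 1.33 to 4.0, and the reversed 0.75 and 0.50, rest on assumed completeness of recording and an equal true risk, and only show the scale. With about 16 to 17 unexposed children a single event is worth about 6 percentage points.

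Separately, 9.2.7.4 and Table 4 note e disagree about what governs growth assessment in untreated children. That is an inconsistency in current text and needs no assumption.

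**What to change.** In 9.7.3.4 and the SAP:

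- Keep investigator-reported PPC in both cohorts. Give its frequency among all growing children and also among those with open epiphyses at index and at least one later assessable epiphyseal status.
- Beside it, show by cohort the number of children assessed and the epiphyseal assessments per child-year.
- Add a supplementary table, derived identically in both cohorts, of the first change in recorded status from open to partially closed or closed, with chronological age, bone age and sex at the change. Label it as including physiological closure; it does not replace the PPC endpoint.

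In the protocol text, reconcile 9.2.7.4 with Table 4 note e, and name exposure-dependent ascertainment in 9.9.

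The cost is a few derivations and tables from variables already collected (epiphyseal status, bone age, date of birth, sex) and two text edits, with no added imaging. The downsides are smaller denominators, sparse cells in the unexposed cohort, and a date of first recorded change that still depends on how often children are imaged. The assessment counts make that last dependence visible but do not remove it.

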**PAGE 41 OF 287** 

 Table 3
 Schedule of Assessments: Exposed Non-naïve Participants

Assessment/Procedure	Retrospective Period (From first marketed palovarotene intake)	Baseline Visit	Follow-Up Visits (as per routine clinical practice[a])/ End of Study Visit
Clinic visit or telephone/video contact visit		X	X
Informed consent [b]		X	
Inclusion/exclusion criteria		X	
Baseline demographics		X	
Physical examination [c,d]	X [p]	X	X
Medical or surgical history	X		
FOP history	X		
Growth status assessment (bone age, knee height and epiphyseal status) [d,e]	X [p]	X	X
Tanner staging	X [p]	X	X
Linear height [f] and weight [d]	X	X	X
Vital signs [d,g]	X [p]	X	X
Pregnancy testing [h]		X	X
Prior /concomitant medications [i]	X	X	X
Concomitant surgery and non-drug therapies	X	X	X
Prior use of palovarotene (investigational product)	X		
Palovarotene dose for chronic and flare-up treatment [j]	X	X	X
Spirometry and DLCO test [d,k]	X [p]	X	X
CAJIS [d]	X [p]	X	X
Movement mobility history (including flare-ups [l])	X		
Movement mobility changes (including flare-ups)		X	X
Spinal health assessment [m]	X [p]		X
Retrospective important medical events related to the disease (including vertebral fractures)	X		
AEs SAEs, Special Situations and AESIs [n]		X	X
Participant Questionnaires:			·
FOP-PFQ assessment [o]		X	X
PROMIS Global Health Scale [o]		X	X
FOP assistive devices assessment [o]		X	X

